### **7.2.5. Follow-Up**

After completion of the Tapering Period, subjects will enter the Follow-Up Period, during which subjects will be treated prophylactically with the rFVIIIFc dose and interval prescribed by the Investigator, according to the label and clinical response of the subject, for 32 weeks (8 months). To avoid bleeding episodes and a relapse of the inhibitors, FVIII activity levels should be kept  $\geq 1$  IU/dL.

If the subject experiences a bleeding episode during the Follow-Up Period, the treatment of the bleed will be left to the discretion of the Investigator. Treatment with bypassing agents may be considered if bleeding is unresponsive to treatment with rFVIIIFc. Subjects with bleeding episodes during the Follow-Up Period will be tested for recurrence of inhibitors (see Section [7.2.2.1](#)).

During the Follow-Up Period, the subject will visit the clinic every 12 weeks (3 months) and undergo procedures and assessments as per the schedule of activities (see [Table 2](#)). At each visit, samples for inhibitor titer and IR assessments will be drawn to monitor for relapse. A subject with confirmed relapse criteria will complete the EOT Visit as soon as possible.

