**Table 2: Schedule of Activities for the Tapering and Follow-Up Periods After Successful Tolerization**

Activities	Tapering Period 	Follow-Up Period 	EOT 	
	Tapering Initiation Visit/Telephone Call,  Week 2, 4, 8, 12, and 16 Visits	Week 28 and 40 Visits 	EOT Visit	Final Safety Follow-Up
	Starting at ITI success and continuing for a minimum of 16 weeks with visits after 2 weeks ( $\pm 3$ days), 4 weeks ( $\pm 1$ week), and then every 4 th week ( $\pm 1$ week)	Week 28 and 40 visits ( $\pm 2$ weeks)  following ITI success	Week 48 visit ( $\pm 2$ weeks) following ITI success OR upon relapse	7 to 14 days after EOT Visit
Physical Examination	X	X	X	
Height (cm)			X	
Weight (kg)	X	X	X	
Vital Signs 	X	X	X	
Hematology (Local Laboratory) 	X		X	
Blood Chemistry (Local Laboratory) 	X		X	
Urinalysis (Local Laboratory) 	X		X	
Nijmegen-Modified Bethesda Inhibitor Assay (Both Local and Central Laboratories) 	X	X	X	
Anti-rFVIIIFc Antibody (ADA) (Central Laboratory)	X	X	X	

CONFIDENTIAL

The information contained herein may not be used, disclosed, or published without the written consent of Bioverativ Therapeutics Inc.

Activities	Tapering Period 	Follow-Up Period 	EOT 	
	Tapering Initiation Visit/Telephone Call,  Week 2, 4, 8, 12, and 16 Visits	Week 28 and 40 Visits 	EOT Visit	Final Safety Follow-Up
	Starting at ITI success and continuing for a minimum of 16 weeks with visits after 2 weeks ( $\pm 3$ days), 4 weeks ( $\pm 1$ week), and then every 4 th week ( $\pm 1$ week)	Week 28 and 40 visits ( $\pm 2$ weeks)  following ITI success	Week 48 visit ( $\pm 2$ weeks) following ITI success OR upon relapse	7 to 14 days after EOT Visit
Blood Sample for Immune Cell Characterization (Required) (Central Laboratory) 	X		X	
rFVIIIFc Dosing 	X	X	X	
FVIII Activity for IR (Both Local and Central Laboratories) 	X	X		
FVIII Activity for $t_{1/2}$ Evaluation (Both Local and Central Laboratories) 			X	
FVIII Activity Level (Both Local and Central Laboratories) 		X	X	
EPD Review, Including Review of Bleeding Episodes and rFVIIIFc Dosing Accountability 	X	X	X	
Nonserious Adverse Events	X	X	X	X
Serious Adverse Events	X	X	X	X

CONFIDENTIAL

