The information contained herein may not be used, disclosed, or published without the written consent of Bioverativ Therapeutics Inc.

Page 27

Activities	Tapering Period 	Follow-Up Period 	EOT 	
	Tapering Initiation Visit/Telephone Call,  Week 2, 4, 8, 12, and 16 Visits	Week 28 and 40 Visits 	EOT Visit	Final Safety Follow-Up
	Starting at ITI success and continuing for a minimum of 16 weeks with visits after 2 weeks ( $\pm 3$ days), 4 weeks ( $\pm 1$ week), and then every 4 th week ( $\pm 1$ week)	Week 28 and 40 visits ( $\pm 2$ weeks)  following ITI success	Week 48 visit ( $\pm 2$ weeks) following ITI success OR upon relapse	7 to 14 days after EOT Visit
Concomitant Therapy/ Procedures Recording	X	X	X	X

Abbreviations: EOT=End of Treatment; EPD=electronic patient diary; ET=early termination; FVIII=coagulation factor VIII; IR=incremental recovery; ITI=immune tolerance induction; PK=pharmacokinetic; rFVIIIFc=recombinant coagulation factor VIII Fc fusion protein;  $t_{1/2}$ =half-life.

NOTE: inhibitor titer, FVIII activity level,  $t_{1/2}$ , and IR are all assessed at the local laboratory, with confirmation by the central laboratory. The Investigators will use local laboratory results for decision-making purposes.

Hematology, blood chemistry, and urinalysis are assessed only at the local laboratory.

- 1 During the Tapering and Follow-Up Periods, the subject's dose will be adjusted to achieve each subject's prophylactic dose as determined by the Investigator. Minimum Tapering Period is 16 weeks (4 months). Subjects who relapse during the Tapering Period (i.e., who have confirmation of inhibitor development AND who have confirmed decrease of IR, with or without clinical signs or symptoms) will proceed immediately to the EOT Visit. Subjects will be closely monitored during the Tapering Period for potential relapse.  
For Canada specific requirements: see Appendix B.
- 2 Timing of the EOT Visit will vary for subjects, as described in Section 7.2.6.

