### 7.2. Overall Study Duration and Follow-Up

The study period will consist of 4 periods: 1) a 4-week (1-month) Screening Period; 2) a maximum of a 48-week (12-month) ITI Period; 3) a minimum of a 16-week (4-month) Tapering Period after all criteria for tolerization have been met; and 4) a 32-week (8-month) Follow-Up Period. The length and the dosing schedules during the Tapering Period are left to the discretion of the treating physician. Only subjects who achieve ITI success will enter the Tapering and Follow-Up Periods. During the Tapering and Follow-Up Periods, the subject's dose will be adjusted with the aim of tapering the dose to reach the prophylactic dosing regimen within at least 12 weeks (3 months) (see [Table 5](#)).

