### **7.2.4. Tapering Period**

Subjects who have met the criteria for ITI success will enter the Tapering Period. Further details about the recommended dosing regimen for tapering are described in Section 11. Subjects with bleeding episodes during the Tapering Period will be tested for recurrence of inhibitors and monitored for relapse.

During the Tapering Period, treatment with bypassing agents may be considered if bleeding is unresponsive to treatment with rFVIIIFc (see Section 7.2.2.1). Testing for recurrence of inhibitors will be performed throughout the Tapering and Follow-Up Periods.

Subjects will visit the clinic 2 and 4 weeks after the first visit in the Tapering Period and then every fourth week for a minimum of 16 weeks (4 months). The duration of the Tapering Period may be modified by the Investigator with the Sponsor Medical Monitor's approval based on the subject's clinical response. If the Tapering Period exceeds 16 weeks (4 months), unscheduled visits will be performed every 4 weeks (1 month) or per the Investigator's judgment.

During the Tapering Period, subjects will undergo procedures and assessments at designated visits per the schedule of events (see Table 2). At each visit, samples for inhibitor titer and IR assessments will be drawn and sent to the local and central laboratories to monitor for relapse.

If the subject experiences bleeding during the Tapering Period, the treatment of the bleeding will be left to the discretion of the Investigator. During the Tapering Period, treatment with bypassing agents may be considered if bleeding is unresponsive to treatment with rFVIIIFc (see Section 7.2.2.1).

Throughout the Tapering Period, rFVIIIFc administration, bypassing agent administration, and any bleeding episodes will be collected by the subject and/or his caregiver in the EPD. The EPD data will be reviewed by the Investigator on an ongoing basis and discussed with the subject at each visit.

CONFIDENTIAL

The information contained herein may not be used, disclosed, or published without the written consent of Bioverativ Therapeutics Inc.

Page 44

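### After ITI success the protocol dates end of treatment in two ways that diverge for tapers longer than about 18 weeks, and the SAP counts relapse to the last visit without the 48-week cut that its objective names

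*Protocol*

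**What the plan says.** **Anchor at the end of tapering.** Protocol 7.2.5: "After completion of the Tapering Period, subjects will enter the Follow-Up Period", where prophylaxis is given "according to the label and clinical response of the subject, for 32 weeks (8 months").

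**Anchor at ITI success.** Protocol Table 2 places the Follow-Up visits at Weeks 28 and 40, and EOT at a Week 48 visit with a window of ±2 weeks, all counted from success: "following ITI success OR upon relapse".

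**Length of tapering.** Protocol 7.2 gives "a minimum of a 16-week (4-month) Tapering Period after all criteria for tolerization have been met" and no maximum, and adds: "The length and the dosing schedules during the Tapering Period are left to the discretion of the treating physician". Section 7.2.4 lets the investigator modify the duration with the Medical Monitor's approval and plans for the long case: "If the Tapering Period exceeds 16 weeks (4 months), unscheduled visits will be performed every 4 weeks (1 month") or as the investigator judges.

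**Cross-reference.** Table 2, footnote 2: "Timing of the EOT Visit will vary for subjects, as described in Section 7.2.6". Section 7.2.6 covers the half-life test at EOT and diary review. It contains no timing rule.

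**Analysis window.** Protocol 6.2 and SAP Table 1 state the relapse and bleeding objectives over the 48 weeks after successful ITI. SAP 4.1 ends the Follow-Up period on the day of the last study visit. SAP 4.4.1.1 and 4.4.1.2 define relapse as the proportion of successes who relapse in Tapering, in Follow-Up and in both combined, with no cut at Week 48.

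**The concern.** When a taper runs well past 16 weeks, a site cannot give the full 32-week Follow-Up and also hold EOT in the Table 2 window. The text does not say which gives way, and the footnote that should settle it leads nowhere. Two sites could read the text differently and stop comparable patients at different times.

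The statistical consequence is for relapse. A crude proportion rises with time under observation. If some patients are followed to Week 48 and others to Week 56 or later, the reported figure mixes unequal exposure, and a relapse after Week 48 is counted under an objective that stops at Week 48. The documents do not require that result to be separated out.

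**Working it through.** **Inputs.** Minimum taper 16 weeks (Protocol 7.2). Follow-Up 32 weeks from the end of tapering (7.2.5). EOT at Week 48, window 46 to 50, from ITI success (Table 2). Lag L from success to the start of tapering: 0 if tapering is counted from success, as the Table 2 column states. L is 2 weeks if it is counted from a Tapering Initiation Visit 2 weeks after the half-life visit (7.2.3), which fits SAP 4.1, where the period starts at the first tapering visit.

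**Reproducing the plan's figure.** 16 + 32 = 48, so the two anchors agree at the minimum taper with L = 0. The stated maximum duration of about two years also reproduces: 4 (screening) + 48 (ITI) + 48 + 2 (safety contact) = 102 weeks; 102 × 7 / 365.25 = 1.95 years.

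**General case.** For a taper of T weeks, 7.2.5 gives EOT week = L + T + 32. Table 2 with L = 0 leaves Follow-Up = 48 − T.

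| Taper T (weeks) | EOT under 7.2.5, L = 0 | Inside 46–50? | Follow-Up if EOT is Week 48, L = 0 | EOT under 7.2.5, L = 2 | Inside 46–50? |
|---|---|---|---|---|---|
| 16 | 48 | yes | 32 | 50 | yes |
| 18 | 50 | yes | 30 | 52 | no |
| 20 | 52 | no | 28 | 54 | no |
| 24 | 56 | no | 24 | 58 | no |
| 32 | 64 | no | 16 | 66 | no |

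Both rules can be met while L + T + 32 ≤ 50: T ≤ 18 with L = 0, and T ≤ 16 with L = 2. In the second case there is no slack above the minimum.

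**Example, T = 24, L = 0.** Either Follow-Up is 24 weeks, 24/32 = 75% of the stated length (26 weeks if the full +2 is used), or EOT is Week 56, 56/48 = 1.17 times the objective's window.

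**Effect on a crude relapse proportion (illustration).** Take a constant hazard and an assumed 48-week risk p, which the documents do not give. The risk by week w is 1 − (1 − p)^(w/48).

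| Assumed p at Week 48 | Week 56 | Week 64 |
|---|---|---|
| 10% | 11.6% | 13.1% |
| 20% | 22.9% | 25.7% |
| 30% | 34.0% | 37.8% |

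These are risks for a patient observed that long. The shift in the study proportion depends on how many patients have long tapers.

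**One patient's weight.** The protocol plans up to 17 subjects, and only successes enter tapering, so one late relapse moves the proportion by at least 1/17 = 5.9 percentage points. SAP section 2 still gives 30, for which the figure is 1/30 = 3.3 points.

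**The case against.** The case for leaving the text alone has four parts.

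- **One reading is favoured.** A long taper adds unscheduled visits, and Protocol 7.3 says these do not move the regular schedule. Section 7.2.5 also refers to Table 2 for procedures. That leans toward the Table 2 calendar, with 32 weeks as what remains after a 16-week taper. It does lean that way, but no passage withdraws the 32 weeks that 7.2.5 states outright.
- **Long tapers may be rare.** Section 11.1 aims to reach prophylaxis within 16 weeks, the Table 5 example does so, and a changed duration needs approval. This stands as a limit on frequency. The documents give no distribution of taper lengths.
- **Bleeding is handled.** Protocol 16.2.2.2 annualizes the rate expressly because period lengths may differ, and SAP 4.4.1.2 does likewise. This largely stands, although annualizing does not restrict the data to 48 weeks.
- **Late relapses will be visible.** SAP 4.3.4 lists each patient's time in Tapering and Follow-Up and time from success to relapse. SAP 4.1 also promises Kaplan-Meier estimates for event times in general. The listing helps a reader but leaves the summary proportion unchanged. The Kaplan-Meier rule is written for the ITI analysis set, and the relapse section plans time to relapse only among those who relapsed.

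A reader might also infer three stronger points that the documents do not support:

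- *That 7.2.5 fails to deliver the 48-week window.* Observation to Week 56 contains all of Weeks 0 to 48. The problem is unequal extra time without a cut.
- *That no visit is scheduled after Week 48.* Section 7.2.5 has visits every 12 weeks. Counted from the end of a 24-week taper they fall at Weeks 36 and 48 with EOT at 56; after a 32-week taper, at Weeks 44 and 56 with EOT at 64.
- *That the two-year duration is contradicted.* With a 24-week taper, 4 + 48 + 56 = 108 weeks before the safety contact, or 2.07 years, which still fits an approximate figure.

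**Conclusion.** The contradiction is real and sits in the current text. It bites for tapers longer than 18 weeks counted from ITI success, or longer than 16 weeks counted from a Tapering Initiation Visit 2 weeks later. For a 24-week taper the two rules are 8 weeks apart.

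It would be too strong to say that the post-success window is undefined: the objectives state 48 weeks. What is not fixed is the window observed and analysed, because the SAP runs to the last study visit. The exposed result is the crude relapse proportion, a secondary endpoint. Bleeding is affected less, and the primary endpoint not at all. The size in this trial cannot be computed, since the number of long tapers is unknown. The relapse percentages rest on an assumed baseline risk and a constant hazard. In a study this small, a single late relapse would be enough to change the reported figure visibly.

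**What to change.** **Protocol.** Reconcile Sections 7.2.4, 7.2.5 and 7.2.6 with Table 2 and its footnote 2 on one anchor for the Follow-Up visits and EOT, and state the timing in 7.2.6, where the footnote points. State also whether tapering is counted from ITI success or from the Tapering Initiation Visit. Which schedule applies is for the sponsor to decide.

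**SAP.** For the 48-week objectives, count relapse and bleeding from ITI success to Week 48, including the visit window, and report later events and later observation time separately. Say whether the first or the confirmatory assessment dates a relapse, so that one confirmed just after Week 48 is placed without ambiguity.

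**Cost.** A protocol clarification and one or two SAP sentences. No new assessments are needed if the Table 2 schedule stands, and the dates required are already planned for the patient listing in SAP 4.3.4.

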### **7.2.6. End of Treatment/End of Study**

At the EOT Visit, PK assessments to determine rFVIIIFc  $t_{1/2}$  will be performed.  $t_{1/2}$  determination at EOT Visit does not need to be performed if the full 4-sample  $t_{1/2}$  assessment was performed within 2 weeks prior to the EOT Visit or if the Investigator determines the subject is an ITI Treatment Failure (see Section [7.2.2.2](#)). Throughout the Follow-Up Period, rFVIIIFc

CONFIDENTIAL

The information contained herein may not be used, disclosed, or published without the written consent of Bioverativ Therapeutics Inc.

Page 45

administration and any bleeding episodes will be collected by the subject and/or his caregiver in the EPD. The EPD data will be reviewed by the Investigator on an ongoing basis and discussed with the subject at each visit.

#### **7.2.7. Final Safety Follow-Up**

A Final Safety Follow-Up Visit or Follow-Up Telephone Call will take place within 7 to 14 days after the EOT Visit to monitor AEs, SAEs, and concomitant medications and procedures.

#### **7.3. Unscheduled Visits**

Subjects may return for an evaluation any time their condition warrants medical attention or to repeat safety assessments, protocol-required assessments, including evaluations of inhibitor, IR or PK, or any blood sampling, as necessary for study purposes. An unscheduled visit will not affect the regular visit schedule and assessments.

#### **7.4. Study Stopping Rules**

Sponsor may terminate this study at any time, after informing the Investigator(s). Sponsor will notify Investigator(s) if the study is placed on hold, completed, or terminated.

Sponsor may also stop the study for futility and not meeting the enrollment targets.

#### **7.5. End of Study**

The end of study is defined as last subject, last visit for final collection of data.

CONFIDENTIAL

The information contained herein may not be used, disclosed, or published without the written consent of  
Bioverativ Therapeutics Inc.

Page 46

VV-CLIN-0542000 3.0

## 8. SELECTION OF SUBJECTS

### 8.1. Inclusion Criteria

To be eligible to participate in this study, candidates must meet the following eligibility criteria at the time of enrollment:

1. Ability of the subject or his legally authorized representative (e.g., parent or legal guardian) to understand the purpose and risks of the study and provide signed and dated informed consent and authorization to use protected health information in accordance with national and local subject privacy regulations
2. Male subjects of any age diagnosed with severe hemophilia A (as confirmed from the medical record)
3. Currently diagnosed with high-titer inhibitors (historical peak  $\geq 5$  BU/mL, according to medical records)
4. Previously treated with any pd-FVIII or recombinant conventional or Extended Half-Life FVIII
5. Canada specific requirements: See Appendix B.

### 8.2. Exclusion Criteria

Candidates will be excluded from study entry if any of the following exclusion criteria exist at the time of enrollment:

1. Other coagulation disorder(s) in addition to hemophilia A
2. Previous ITI
3. History of hypersensitivity or anaphylaxis associated with any FVIII administration
4. Planned major surgery scheduled during the study unless deferred until after study completion (minor surgery such as tooth extraction or insertion/replacement of central venous access device is allowed)
5. Abnormal renal function (serum creatinine  $>1.5$  mg/dL or  $2 \times$  upper limit of normal (ULN) for subject age based on local laboratory range) as assessed by local laboratory
6. Serum alanine aminotransferase or aspartate aminotransferase  $>5 \times$  ULN as assessed by local laboratory
7. Serum total bilirubin  $>3 \times$  ULN as assessed by local laboratory
8. Current enrollment or a plan to enroll in any interventional clinical study in which an investigational treatment or approved therapy, other than rFVIIIFc, for investigational use is administered within 30 days (or 5 half-lives of the agent, whichever is longer) prior to the Baseline Visit
9. Inability to comply with study requirements

CONFIDENTIAL

The information contained herein may not be used, disclosed, or published without the written consent of  
Bioverativ Therapeutics Inc.

Page 47

10. Presence of any medical or psychological condition or laboratory result that, in the opinion of the Investigator, can interfere with the subject's ability to comply with the protocol requirements or make the subject not appropriate for inclusion to the study and treatment with Elocta®/Eloctate® (rFVIIIFc)
11. Other unspecified reasons that, in the opinion of the Investigator or Sponsor, make the subject unsuitable for enrollment
12. Unwillingness or inability to comply with the requirements of the protocol, including the presence of any condition (physical, mental, or social) that prevents the subject from participating in visits as scheduled or entering required information into the EPD in a timely manner
13. Concurrent systemic treatment with immunosuppressive drugs within 12 weeks (3 months) prior to Screening. Exceptions to this include ribavirin for treatment of hepatitis C virus (HCV), and/or systemic steroids (a total of 2 courses of pulse treatments lasting no more than 7 days within 12 weeks [3 months] prior to Day 1) and/or inhaled steroids
14. High risk of cardiovascular, cerebrovascular, or other thromboembolic events, as judged by the Investigator

The following criteria refer to tests performed within 26 weeks (6.5 months) prior to Screening. If not available, a new test will be drawn at the Screening Visit.

15. Cluster of differentiation 4 (CD4) lymphocytes  $<200 \text{ mm}^3$  at Screening, if known as human immunodeficiency virus (HIV) antibody positive based on medical history or HIV testing
16. Viral load of  $>400 \text{ copies/mL}$  at Screening, if known as HIV antibody positive based on medical history

CONFIDENTIAL

The information contained herein may not be used, disclosed, or published without the written consent of  
Bioverativ Therapeutics Inc.

Page 48

VV-CLIN-0542000 3.0

## **9. ENROLLMENT AND REGISTRATION, STUDY PROCEDURES**

Once the investigational site has been activated for study participation, subjects may be enrolled if they have met the inclusion criteria in Section 8.1 and have not been excluded based on the exclusion criteria in Section 8.2.

### **9.1. Screening, Enrollment**

Subjects or their legally authorized representative (e.g., parent or legal guardian), where applicable, must provide informed consent before any Screening tests or assessments are performed. Participating study sites are required to register all screened candidates in this study in the IXRS. If a subject is excluded from the study, the reasons for exclusion will be documented in the subject's documents.

### **9.2. Registration of Subjects**

At the Screening Visit, IXRS will be used to assign each subject a unique 6-digit subject identification number (see Section 19.1.2). No subject may begin treatment prior to enrollment. Subject identification numbers that have been assigned will not be reassigned to another subject, even if the subject does not receive treatment. If a subject is rescreened, the subject may use his original number.

See the Study Reference Manual for details on registration.

CONFIDENTIAL

The information contained herein may not be used, disclosed, or published without the written consent of  
Bioverativ Therapeutics Inc.

Page 49

VV-CLIN-0542000 3.0

